9.4 Definition of Dose-Limiting Toxicity (DLTs)

The period of DLT monitoring will be 6 weeks beginning from the first durvalumab dose administered. Patients who are removed from the study for reasons other than DLT prior to the administration of the first Thyrogen injection will be replaced with another subject. Patients who do not complete the 6 week period of monitoring beginning from the first durvalumab dose for reasons other than DLT will also be replaced. Grading of DLTs will follow the guidelines provided in the Common Terminology Criteria for Adverse Events (CTCAE) version 4.0.

If >1 of the first 3 patients or >2 of the first 6 patients develop a DLT related to durvalumab, further accrual to the study will be halted. If this threshold is not crossed, 11 patients in total will be accrued to the pilot study.

With the exception of specific AEs discussed below, a DLT will be defined as any Grade 3 or higher toxicity that occurs during the DLT evaluation period felt to be possibly, probably, or definitely related to durvalumab. For >Grade 3 adverse events that occur in patients during the DLT monitoring period, investigators must use their discretion to decide if the adverse event is a DLT (e.g., alkaline phosphatase elevation in the context of known progression of hepatic and/or bone metastases might be attributed to progression of disease per investigator discretion).

Any AE requiring discontinuation of durvalumab will also be considered a DLT. Durvalumab-related AEs that occur during the 6-week DLT evaluation period and delay the administration of the second durvalumab dose and/or Thyrogen/RAI therapy by more than two weeks will also be considered DLTs.

Toxicity that is clearly and directly related to the primary disease or to another etiology is excluded from this DLT definition.

The following will be DLTs:

- Any Grade 4 immune related Adverse Event (irAE)
- Any \geq Grade 3 colitis
- Any \geq Grade 3 noninfectious pneumonitis
- Any \geq Grade 3 nephritis or renal dysfunction (elevated serum creatinine)
- Any Grade 2 pneumonitis that does not resolve to \leq Grade 1 within 3 days of the initiation of maximal supportive care
- Any Grade 3 irAE (excluding colitis, pneumonitis, thyroiditis, or nephritis) that does not downgrade to Grade 2 within 3 days after onset of the event despite optimal medical management, including systemic corticosteroids, or does not downgrade to \leq Grade 1 or baseline within 14 days
- Liver transaminase elevation $> 8x$ ULN or total bilirubin $> 5x$ ULN
- Any \geq Grade 3 non-irAE, except for the exclusions listed below

The DLT definition excludes the following conditions:

- Grade 3 fatigue lasting \leq 7 days
- Any grade hypothyroidism or elevation of TSH
- Grade 3 endocrine disorder (pituitary, thyroid, and/or adrenal insufficiency) that is managed with or without systemic corticosteroid therapy and/or hormone replacement therapy and the subject is asymptomatic
- Grade 3 inflammatory reaction attributed to a local antitumor response (e.g., inflammatory reaction at sites of metastatic disease, lymph nodes, etc)
- Concurrent vitiligo or alopecia of any AE grade
- Grade 3 infusion-related reaction (first occurrence and in the absence of steroid prophylaxis) that resolves within 6 hours with appropriate clinical management
- Grade 3 or 4 neutropenia that is not associated with fever or systemic infection that improves by at least 1 grade within 3 days. Grade 3 or Grade 4 febrile neutropenia will be a DLT regardless of duration or reversibility
- Grade 3 or 4 lymphopenia
- Grade 3 thrombocytopenia that is not associated with clinically significant bleeding that requires medical intervention, and improves by at least 1 grade within 3 days
- Isolated Grade 3 electrolyte abnormalities that are not associated with clinical signs or symptoms and are reversed with appropriate maximal medical intervention within 3 days

The following toxicities are excluded from the definition of DLT if observed within 30 days of RAI administration:

- Grade 3 low white blood cell count
- Grade 3 or 4 neutropenia
- Grade 3 thrombocytopenia

Regarding immunosuppression, the laboratory parameter for DLT determination will be absolute neutrophil count (not total white blood cell count).

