Maximum time from needle puncture to start of administration	4 hours at room temperature, 24 hours at 2°C to 8°C
Maximum time for IV bag infusion, including interruptions	8 hours at room temperature

In the event that either preparation time or infusion time exceeds the time limits outlined above, a new dose must be prepared from new vials. Durvalumab does not contain preservatives, and any unused portion must be discarded.

Monitoring of dose administration

Subjects will be monitored before, during and after the infusion with assessment of vital signs at the times specified in the Schedule of Assessment. Subjects are monitored (pulse rate, blood pressure)

approximately every 30 minutes during the infusion period (including times where infusion rate is slowed or temporarily stopped).

In the event of a ≤Grade 2 infusion-related reaction, the infusion rate of study drug maybe decreased by 50% or interrupted until resolution of the event (up to 4 hours) and re-initiated at 50% of the initial rate until completion of the infusion. For subjects with a ≤Grade 2 infusion-related reaction, subsequent infusions may be administered at 50% of the initial rate. Acetaminophen and/or an antihistamine (e.g., diphenhydramine) or equivalent medications per institutional standard may be administered at the discretion of the investigator. If the infusion-related reaction is Grade 3 or higher in severity, study drug will be discontinued. The standard infusion time is one hour, however if there are interruptions during infusion, the total allowed time from infusion start to completion of infusion should not exceed 4 hours at room temperature, with maximum total time at room temperature not exceeding 4 hours (otherwise requires new infusion preparation).

As with any antibody, allergic reactions to dose administration are possible.

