11.1 TOXICITIES/SIDE EFFECTS

For adverse events (AEs) that are considered related to administration of durvalumab, the following may be applied:

- Following the first dose of durvalumab, subsequent administration of durvalumab can be modified based on toxicities observed (see **Appendix 1**). Dose reductions are not permitted.
- Treat each of the toxicities with maximum supportive care (including holding the agent suspected of causing the toxicity where required).
- If the symptoms promptly resolve with supportive care, consideration should be given to continuing the same dose of durvalumab along with appropriate continuing supportive care according to guidelines outlined in **Appendix 1**.
- If modification of durvalumab treatment is required prior to the administration of RAI, delay in giving Thyrogen and RAI therapy prior to the second dose of durvalumab is allowed if the patient remains on study.
- In addition, there are certain circumstances in which durvalumab should be permanently discontinued.
- Cycle 2 and 3 doses of durvalumab will not be held for hematologic cytopenias (leukopenia, anemia, neutropenia, thrombocytopenia), which can occur following RAI therapy.
- Re-starting of durvalumab administration after holding therapy for toxicity can be done at the investigator's discretion as long as criteria in **Appendix 1** are fulfilled. The week that durvalumab is re-started will then be considered to be Week 1. Subsequent treatments and evaluations can then be scheduled accordingly.

Based on the mechanism of action of durvalumab leading to T-cell activation and proliferation, there is the possibility of observing immune related Adverse Events (irAEs) during the conduct of this study. Potential irAEs include immune-mediated enterocolitis, dermatitis, hepatitis, and endocrinopathies. Subjects should be monitored for signs and symptoms of irAEs. In the absence of an alternate etiology (e.g., infection or PD) signs or symptoms of enterocolitis, dermatitis, hepatitis, and endocrinopathy should be considered to be immune-related.

Dose modification recommendations and toxicity management guidelines for immune-mediated reactions, for infusion-related reactions, and for non-immune-mediated reactions related to durvalumab are detailed in Appendix 1. In addition, management guidelines for adverse events of special interest (AESIs) are detailed in **Appendix 1**. All toxicities will be graded according to NCI CTCAE v4.0.

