
Note: For Grade ≥ 3 asymptomatic amylase or lipase levels, hold study drug/study regimen, and if complete work up shows no evidence of pancreatitis, study drug/study regimen may be continued or resumed.
 
Note: Study drug/study regimen should be permanently discontinued in Grade 3 events with high likelihood for morbidity and/or mortality – e.g., myocarditis, or other similar events even if they are not currently noted in the guidelines. Similarly, consider whether study drug/study regimen should be permanently discontinued in Grade 2 events with high likelihood for morbidity and/or mortality – e.g., myocarditis, or other similar events even if they are not currently noted in the guidelines – when they do not rapidly improve to Grade <1 upon treatment with systemic steroids and following full taper
 
Note: There are some exceptions to permanent discontinuation of study drug for Grade 4 events (i.e., hyperthyroidism, hypothyroidism, Type 1 diabetes mellitus).
	
formerly known as Pneumocystis carinii pneumonia) prophylaxis, gastrointestinal protection, and glucose monitoring.
 
– Discontinuation of study drug/study regimen is not mandated for Grade 3/Grade 4 inflammatory reactions attributed to local tumor response (e.g., inflammatory reaction at sites of metastatic disease and lymph nodes). Continuation of study drug/study regimen in this situation should be based upon a benefit-risk analysis for that patient.

AE Adverse event; CTC Common Toxicity Criteria; CTCAE Common Terminology Criteria for Adverse Events; imAE immune-mediated adverse event; IV intravenous; NCI National Cancer Institute; PO By mouth.

Pediatric Considerations

Dose Modifications	Toxicity Management

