Grade 3 or 4	
For Grade 3 or 4 endocrinopathy other than hypothyroidism and Type 1 diabetes mellitus, hold study drug/study regimen dose until endocrinopathy symptom(s) are controlled.
 
Study drug/study regimen can be resumed once event stabilizes and after completion of steroid taper.
 
Patients with endocrinopathies who may require prolonged or continued steroid replacement (e.g., adrenal insufficiency) can be retreated with study
	For Grade 3 or 4: 
– Consult endocrinologist to guide evaluation of endocrine function and, as indicated by suspected endocrinopathy and as clinically indicated, consider pituitary scan. Hospitalization recommended.– For all patients with abnormal endocrine work up, except those with isolated hypothyroidism or Type 1 DM, and as guided by an endocrinologist, promptly initiate empiric IV methylprednisolone 1 to 2 mg/kg/day or equivalent, as well as relevant hormone replacement (e.g., hydrocortisone, sex hormones).– For adrenal crisis, severe dehydration, hypotension, or shock, immediately initiate IV corticosteroids with mineralocorticoid activity.– Isolated hypothyroidism may be treated with replacement therapy, without study drug/study regimen interruption, and without corticosteroids.

			
 – drug/study regimen on the following conditions: 
 1. The event stabilizes and is controlled. 2. The patient is clinically stable as per investigator or treating physician's clinical judgement. 3. Doses of prednisone are ≤ 10 mg/day or equivalent. – Isolated Type 1 diabetes mellitus may be treated with appropriate diabetic therapy, without study drug/study regimen interruption, and without corticosteroids. – Once patients on steroids are improving, gradually taper immunosuppressive steroids (as appropriate and with guidance of endocrinologist) over ≥ 28 days and consider prophylactic antibiotics, antifungals, and anti-PJP treatment (refer to current NCCN guidelines for treatment of cancer-related infections [Category 2B recommendation]).^a

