Grade 1 or 2	For Grade 1: 
The infusion rate of study drug/study regimen may be decreased by 50% or temporarily interrupted until resolution of the event.
 For Grade 2: 
The infusion rate of study drug/study regimen may be decreased 50% or temporarily interrupted until resolution of the event.
 
Subsequent infusions may be given at 50% of the initial infusion rate.
	For Grade 1 or 2: 
– Acetaminophen and/or antihistamines may be administered per institutional standard at the discretion of the investigator.– Consider premedication per institutional standard prior to subsequent doses.– Steroids should not be used for routine premedication of Grade ≤ 2 infusion reactions.
Grade 3 or 4	For Grade 3 or 4: 
Permanently discontinue study drug/study regimen.
	For Grade 3 or 4: 
– Manage severe infusion-related reactions per institutional standards (e.g., IM epinephrine, followed by IV diphenhydramine and ranitidine, and IV glucocorticoid).

CTCAE Common Terminology Criteria for Adverse Events; IM intramuscular; IV intravenous; NCI National Cancer Institute.

Non-Immune-Mediated Reactions

Severity Grade of the Event (NCI CTCAE version 4.03)	Dose Modifications	Toxicity Management
Any Grade	Note: Dose modifications are not required for AEs not deemed to be related to study treatment (i.e., events due to underlying disease) or for laboratory abnormalities not deemed to be clinically significant.	Treat accordingly, as per institutional standard.
Grade 1	No dose modifications.	Treat accordingly, as per institutional standard.
Grade 2	Hold study drug/study regimen until resolution to ≤Grade 1 or baseline.	Treat accordingly, as per institutional standard.
Grade 3	Hold study drug/study regimen until resolution to ≤Grade 1 or baseline. For AEs that downgrade to ≤Grade 2 within 7 days or resolve to ≤Grade 1 or baseline within 14 days, resume study drug/study regimen administration. Otherwise, discontinue study drug/study regimen.	Treat accordingly, as per institutional standard.
Grade 4	Discontinue study drug/study regimen (Note: For Grade 4 labs, decision to discontinue should be based on accompanying clinical signs/symptoms, the Investigator's clinical judgment, and consultation with the Sponsor.).	Treat accordingly, as per institutional standard.

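### A first Grade 3 infusion reaction that clears within 6 hours is both excluded from and included in the DLT definition

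*Combined protocol and SAP*

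**What the plan says.** Four statements bear on the same event.

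- Section 9.4, exclusion list: under the lead-in "The DLT definition excludes the following conditions" the plan names a "Grade 3 infusion-related reaction (first occurrence and in the absence of steroid prophylaxis) that resolves within 6 hours with appropriate clinical management".
- Section 9.4, earlier: "Any AE requiring discontinuation of durvalumab will also be considered a DLT". No exception is attached.
- Section 5.2 (Durvalumab), on monitoring of dose administration: "If the infusion-related reaction is Grade 3 or higher in severity, study drug will be discontinued".
- Appendix 1, infusion-related reactions, Grade 3 or 4 row: "Permanently discontinue study drug/study regimen".

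Neither discontinuation rule makes an exception for a first reaction or one that clears quickly.

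Sections 9.4 and 14.0 halt accrual for more than 1 DLT in the first 3 patients or more than 2 in the first 6. The Section 14.0 table adds more than 2 among all 11. Patients who leave before the first Thyrogen injection, or who do not complete the 6-week window, for reasons other than DLT are replaced.

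**The concern.** One event carries two opposite codings in the definition of the primary safety endpoint. Under the exclusion list, a patient permanently taken off durvalumab by a severe drug-related reaction has no DLT. Under the discontinuation sentence, the same patient has one. The halting rule reads only the DLT count, and the thresholds are low enough for one event to matter. One such reaction plus one other DLT in the first 3 patients is either 2 of 3 (halt) or 1 of 3 (continue). The study is single-arm, and whoever codes the event would know both it and the running count.

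There is a possible second effect, which is an inference and not stated in the plan. If the exclusion prevails and the patient leaves before Thyrogen or before week 6, the replacement rule could remove that patient from the DLT denominator as well. The event would still be reported as an adverse event.

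**Working it through.** **1. Do the rules overlap fully?** The excluded event is, by its own wording, a Grade 3 infusion reaction. Section 5.2 and Appendix 1 stop durvalumab for every such reaction, and the discontinuation sentence makes that a DLT. The overlap is therefore total. The exception wording in Section 9.4 is attached to the general Grade 3-or-higher criterion and to the bullet on non-immune Grade 3-or-higher events. The discontinuation sentence stands apart as an additional criterion.

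**2. Is this bullet unusual?** It is the only exclusion whose every occurrence mandates discontinuation:

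- Local antitumour inflammation (Appendix 1): "Discontinuation of study drug/study regimen is not mandated for Grade 3/Grade 4 inflammatory reactions attributed to local tumor response".
- Cytopenias after RAI (Section 11.1): "Cycle 2 and 3 doses of durvalumab will not be held for hematologic cytopenias".
- Hypothyroidism (Appendix 1): "Isolated hypothyroidism may be treated with replacement therapy, without study drug/study regimen interruption".
- Short Grade 3 non-immune events may resume, and Grade 4 laboratory values are left to judgement (Appendix 1).

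**3. Reproducing the plan's operating characteristics.** Patients enter as 3 + 3 + 5, with DLT probability p. At p = 0.10:

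- First look, at least 2 of 3: 3(0.1²)(0.9) + 0.1³ = 0.0280.
- Second look, at least 3 of 6 without crossing earlier: 0.729 × 0.001 + 0.243 × 0.028 = 0.0075.
- Final, at least 3 of 11 without crossing earlier: 0.5314 × 0.00856 + 0.3543 × 0.08146 + 0.0787 × 0.40951 = 0.0657.
- Sum: 0.1012, against the stated 0.101184466.

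At p = 0.35 the three parts are 0.2818 + 0.1368 + 0.3890. Unrounded they sum to 0.8075, against the stated 0.80748277. At p = 0.20 the rule gives 0.3987.

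**4. Assumed reaction rate q.** The documents give no rate for Grade 3 infusion reactions. Section 3.0 lists the related Grade 3-or-higher events seen in 3 or more of 694 subjects in Study 1108 (10 mg/kg every 2 weeks). Infusion reaction is not listed, which suggests at most 2 of 694 = 0.29%. Reactions coded under other terms would not show. The range used is 1/694 = 0.14%, 2/694 = 0.29%, and 1.04%, the exact two-sided 95% upper limit for 2/694.

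**5. Effect of counting the reaction.** Assuming independence, the per-patient DLT rate becomes p + q(1 − p). For example, 0.10 + 0.00288 × 0.90 = 0.1026. The rise in the chance of crossing the rule, in percentage points, is:

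| q | p = 10% | p = 20% | p = 35% | At least one in 11, 1 − (1 − q)¹¹ |
|---|---|---|---|---|
| 0.14% | 0.29 | 0.38 | 0.18 | 1.6% |
| 0.29% | 0.59 | 0.76 | 0.35 | 3.1% |
| 1.04% | 2.2 | 2.7 | 1.2 | 10.8% |

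**6. If the reaction does occur.** One DLT alone crosses no boundary at any position. With one such reaction in the first 3 patients, coding decides the first look when exactly one of the other two has a DLT. That probability is 2p(1 − p) = 0.180, 0.320 and 0.455. With one reaction placed at random among the 11, enumeration over the other ten patients shows coding changing the overall verdict with probability about 20%, 30% and 17%.

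**7. Unconditional first-look figure.** At q = 0.29%, the chance of a reaction in the first 3 is 1 − (1 − 0.00288)³ = 0.86%. Multiplying by step 6 gives about 0.16%, 0.28% and 0.39%.

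**The case against.** The strongest reply is that the exclusion list governs. It comes after the discontinuation sentence, its lead-in speaks of the DLT definition as a whole, and a narrow bullet with several qualifiers would ordinarily limit an earlier general sentence. Section 9.4 read alone is consistent, and the collision appears only once Section 5.2 and Appendix 1 are added. That reading is possible, but it is not written down. It leaves the discontinuation sentence untrue for this event, and it fits poorly with the bullet's reference to a first occurrence in a protocol that allows no second exposure.

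The reply is right that the effect is small and the assumed rates generous. The 694-subject listing covers any time on treatment, whereas the disputed event is a quickly resolving first reaction within 6 weeks. The larger pool in Section 3.0 (1,889 patients) lists related Grade 3 or 4 events at 0.5% or more and does not include infusion reactions, which points to a rate below 0.5%. The 1.04% figure is therefore an upper bound. The replacement effect is also uncertain, because stopping the drug need not end the 6-week observation.

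The reply is also fair that the documents do not show which rule the sponsor meant to win, so the direction of the repair is a recommendation. None of this removes the overlap.

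**Conclusion.** The concern holds. The plan gives two incompatible codings for one event in its primary safety endpoint, with no order of precedence. This conclusion rests on the text alone and is firm. Its numerical weight is low. At the central assumed rate the chance of a too-toxic verdict moves by less than 1 percentage point, and at the upper limit by up to 2.7 points. Those figures assume that reactions occur independently of other DLTs and that the Study 1108 listing carries over to 1500 mg every 4 weeks. The event matters if it happens, because its coding can then decide whether accrual halts. The design calculation is correct and needs no change. This should be corrected as a clarification of the endpoint; it does not undermine the design.

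**What to change.** Delete the infusion-reaction bullet from the exclusion list in Section 9.4. Alternatively, add a sentence there stating that the discontinuation criterion overrides the exclusion list. Deletion is cleaner, because an override would leave a bullet that can never apply. Either way the event counts as a DLT, in line with Section 5.2 and Appendix 1. The patient then stays in the denominator under the existing replacement rule.

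The cost is one bullet or one sentence. If such a reaction occurs, the DLT result is slightly less favourable: at the assumed 0.29% rate and a 10% DLT rate from other causes, the chance of a too-toxic verdict rises from 10.1% to 10.7%. A general override would also count a Grade 4 cytopenia for which the investigator chooses to stop durvalumab, which the discontinuation sentence already implies on its face.

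If the sponsor prefers to keep the exclusion, the discontinuation sentence needs an explicit carve-out, so an edit is needed in either case.

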9.5 Correlative Studies

Tumor Analysis: (These studies will be conducted in collaboration with Drs. [name], [name], and [name].)

Exploratory objective: To investigate potential tumor predictors/correlates of benefit to durvalumab plus rhTSH-stimulated/prepared RAI therapy.

Rationale: We hypothesize that interfering with the PD-1/PD-L1 axis in thyroid cancers can result in the loss of tolerance to immunogenic thyroid antigens, which can be augmented by rhTSH stimulated RAI therapy. Other predictors of benefit to immunotherapeutic approaches delineated in other settings include PD-L1 expression, tumor mutation burden, and neoantigen load. To evaluate the potential correlation of these tumor features with the efficacy of durvalumab plus rhTSH-prepared RAI, we will perform whole exome and transcriptome analysis in fresh research biopsies and/or archival tissues.

Of particular importance is the lack of data addressing how immune checkpoint inhibition and RAI therapy impacts the dynamics of the thyroid cancer immune microenvironment and genomic landscape. For the latter, immunotherapy induced changes to the tumor genome could provide insights into the “immunoediting” induced by therapy and potentially identify epitopes of particular significance for efficacy. The only approach that will provide new insight into these biologic processes is the analysis of serial research biopsies performed during therapy. On this study, biopsies will be performed pre-treatment and after durvalumab/RAI in Cycle 2. These tissues will be analyzed with next-generation sequencing of DNA and RNA. For cases in which sufficient tissue is collected, the immune microenvironment may be characterized by cytometric techniques, including flow cytometry or mass cytometry (CyTOF; MIBI). Protein based approaches, including IHC (e.g. for PD-L1, PD-L2 status), will also be employed. We hypothesize that durvalumab and RAI will increase tumoral immune infiltration characterized by enhanced markers of T cell activation (increased granzyme/performin expression, enrichment of the IFN-gamma signaling pathway, decreased Treg/CD8+ ratio). Beyond characterizing the tumor-associated T cell infiltrate, therapy induced changes of other immune cell populations will be examined (e.g. macrophages, NK cells, B-cells). Additionally, how durvalumab/RAI impacts the status of other immune checkpoint molecules (e.g. LAG-3, CTLA-4, TIM-3) may provide insights into putative mechanisms of resistance to this therapeutic approach. Such studies will be essential for rationally developing future immunotherapy based therapeutic approaches for advanced thyroid cancer patients.

Approach: The research biopsy samples will be divided for fixation and flash freezing at the discretion of the Principle Investigator. These samples will be used to evaluate the genomic and transcriptomic landscape of the tumors. Archival tissues may also be used if of sufficient quantity and quality.

DNA and RNA will be extracted from frozen samples and/or paraffin tissue. The research peripheral blood sample collected on the study will be used as a control, matched normal sample (microdissection of normal tissue in the tumor samples may also be used for this purpose). DNA will be submitted for next generation sequencing, possibly whole exome or whole genome sequencing. The specific assay that will be employed to analyze for genomic alterations will be dependent upon the technology available at the time of analysis. Comparisons of DNA between tumor and normal tissue (from the research blood draw) will be performed as appropriate, thus generating germline sequence data. There is no intention to analyze the germline data beyond

utilizing it as a normal control for the tumor tissue analysis, and generally germline data will not be communicated to the patient. This data will be used to quantitate mutation load and identify candidate neoantigens.

Extracted RNA will be analyzed with RNAseq technology, or alternative assays, depending on technical limitations and assay availability. RNAseq data will be used to define a set of expressed neoepitopes and explore gene expression signatures that may correlate with response. RNAseq data analysis may include:

- Quantification of the following: 1) Markers of the MAPK pathway transcriptional output (e.g. Etv1, Etv4, Etv5, Spry2, Spry4, Dusp6); 2) Genes required for thyroid hormone biosynthesis (e.g. Nkx2.1, Pax8, Foxe1, Tg, Tpo, TshR, Nis, Pendrin, Dio2); 3) PD-L1 expression (PD-L1 expression will also be analyzed by IHC).
- Analysis to characterize tumor (a) immune cell infiltration and (b) immunologic gene signatures.

For patients in whom two serial research biopsies are obtained, evolution of the mutation, neoantigen, and gene expression landscape in pre- and post-treatment samples will be analyzed to gain insights into immunoediting that may occur and infer what epitopes may be critical for efficacy. RNAseq data will also be used to explore changes in the expression of nonmutated thyroid gene expression (e.g. TG, THSR, TPO, etc...) with therapy for the same purpose. The same data can be analyzed to evaluate how immune cell tumoral infiltration and immunologic gene signatures may change with therapy.

Frozen tissues from the research biopsy may be evaluated for relevant protein targets by Western blot or other proteomic assays that may be available at time of analysis.

Fixed archival and/or research biopsy tissues may also be evaluated by immunohistochemistry to assess changes in tumor immune infiltrates and tumor/immune cell protein expression (e.g. PD-L1 status). For patients in whom sufficient fresh tissue can be collected in the research biopsies, the tumor immune cell infiltrate (or tumor infiltrating lymphocytes ("TILs") may be extracted and characterized by cytometric techniques, including flow cytometry or mass cytometry (CyTOF).

Note regarding next generation sequencing analysis performed on this protocol: In the course of this research it is possible that some patients whose tumors are analyzed through investigational "next-generation" profiling in a research (non-CLIA) environment will be found to have somatic or germline mutations in genes that are known to be associated with an increased risk of cancer or other diseases. It will be stated in the consent that the participants will not receive any specific results from research tests. The consent will tell participants that if they wish to have genetic testing done for personal reasons than they should make an appointment with the MSK Clinical Genetics Service.

If in the course of this research a research finding is obtained that, in the opinion of the investigator, may be critical to the preventive care of the participant or their family, the investigator can communicate that finding to the IRB Genomic Advisory Panel (GAP). The finding will be reviewed by the GAP to determine whether the incidental finding should be discussed with the participant. For MSK, in the event that the GAP determines that the finding should be discussed with the participant, and the participant has consented to be re-contacted, then the

treating/consenting physician shall be contacted by the panel and asked to refer the participant to the Clinical Genetics Service for further discussion of the research finding.

The following information must be provided to GAP for review:

- Participant Name/MRN #
- Type of Biospecimen (tissue, blood, saliva)
- Incidental Finding
- Collection Protocol #
- Contact: [contact]

Peripheral Blood Analysis:

Exploratory Objective #1: To investigate changes in peripheral blood populations that occur with durvalumab and rhTSH-prepared RAI.

Rationale: We hypothesize that disruption of the PD-1/PD-L1 axis with durvalumab in combination with rhTSH-prepared RAI therapy will alter peripheral blood immune populations. Additionally, T cell receptor repertoire may be analyzed.

Approach: (These studies will be conducted in collaboration with the MSK immune monitoring core facility.) At the time points indicated in **Section 10**, peripheral blood samples will be collected: 4 CPT tubes (BD, 8-ml capacity, total blood volume collected ~32 ml for PBMC purification for flow cytometric analysis) and 1 PAXgene tube (BD order #762165 or equivalent) (for purification of RNA/DNA for TCR analysis). Changes to these methods may be adapted depending upon the most recent, generally accepted protocols. Flow cytometry will be used to evaluate changes in T cell subsets at different time points. Alternative approaches to this analysis may be pursued depending upon the availability of new technologies, platforms, or approaches. Specifically, assays investigating the immunogenicity of tumoral antigens in *ex vivo* assays utilizing these collected PBMCs may be of value and will be performed to identify potential neoantigens or self antigens that are critical for mediating therapeutic efficacy.

Exploratory Objective #2: To investigate changes in cell free DNA (cfDNA) that occur with durvalumab and rhTSH-prepared RAI.

Rationale: We hypothesize that rhTSH-prepared RAI therapy will enhance expression and release of thyroid-specific antigens/neoantigens critical for augmenting immunotherapeutic responses to PD-L1 targeting with durvalumab. Here, we propose using tumor cfDNA as a surrogate marker of tumor lysis and antigen release.

Approach: (These studies will be conducted in collaboration with the MSK Department of Laboratory Medicine, MSK cfDNA extraction facility, and Kravis Center for Molecular Oncology (CMO).) At the time points indicated in **Section 10**, peripheral blood samples will be collected. Whole blood will be collected in 10-ml Cell-Free DNA BCT tubes (STRECK) and centrifuged in two steps to separate plasma from cells. Cell-free plasma will then be aliquoted and frozen at minus 80°C until ready to extract. Extraction of cfDNA will be performed using a fully automated QIAGEN platform, QIAAsymphony SP, and QIAAsymphony DSP Virus/Pathogen Midi Kit (catalog #937055). This is a bead-based custom protocol, optimized to work with 3 ml of plasma as starting material. The extraction process includes lysis, binding, wash and elution steps. The final product is a 60 µl

elution of cfDNA with an average size ~170-200 bp. Quality and quantity of cfDNA will be evaluated with automated electrophoresis using either TapeStation with High Sensitivity D1000 ScreenTape and Reagents (Agilent Technologies) or Fragment Analyzer with High Sensitivity genomic DNA Analysis Kit (Advanced Analytical).

The resulting cfDNA can then be further analyzed to detect and quantify amounts of tumor driver oncogenes (BRAF mutations, RAS mutations, etc...) or other gene mutations if appropriate. These cfDNA results will be analyzed in an exploratory/descriptive manner.

